**Question 8b. Which types of doctors have you been to in hospital for the past 3 months? And how often?**

Which type of doctor did you visit in the hospital?	How often have you been with this doctor in the past 3 months?
example cardiologist	example 2times
.....	.....times
.....	.....times
.....	.....times
.....	.....times
.....	.....times
.....	.....times
.....	.....times

**Question 9a. Have you been hospitalised again in the past 3 months?** In other words, you had to stay overnight.

- No
- Yes

Have you ticked "Yes"? Then answer questions 9b. Otherwise, continue with question 10.

**Question 9b. How long have you been in the hospital?** Have you been in the hospital more than once in the past 3 months? Then add up all the days.

..... days in total in the past 3 months.

**Question 10a. Did you go elsewhere in the past 3 months?** For example, you went to a residential/care centre or a psychiatric institution. Or a rehabilitation centre.

- No
- Yes, but I only went during the day
- Yes, I was admitted there (I stayed there overnight)

Have you ticked "Yes"? Then answer questions 10b and 10c. Otherwise, continue with question 11.

**Question 10b. What kind of institution was this?** Tick the correct answer. You can tick more than 1 box.

- Residential care centre or nursing home
- Rehabilitation centre
- Mental health institution
- Another institution, namely .....

.....

**Question 10c. How many times did you have to go here in the past 3 months?**  
Have you ticked more than one box in question 10b? Then enter the number of days and nights you have been there for each institution below.

To a residential care or nursing home:	..... days and ..... nights in the past 3 months
To the rehabilitation centre:	..... days and ..... nights in the past 3 months
To the mental health institution:	..... days and ..... nights in the past 3 months
To the other institution:	..... days and ..... nights in the past 3 months

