#### **10.5 Other study parameters**

The cost-effectiveness will be calculated by comparing the costs for patients with good functional outcome, costs per QALY and costs for the intervention and hospital admissions. Quality of life will be assessed with the EuroQol-5D-5L. Costs for potential productivity loss will be assessed with a set of questions from the iMTA Productivity Cost Care (iPCQ) and costs for any other relevant healthcare resource use will be measured by a set of questions from the iMTA Medical Consumption Questionnaire (iMCQ).

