#### **How do you have to fill in the list?**

- Start with the first question and follow the numbering.
- For each question, tick 1 box, except if the question states that you can tick more than 1 box.
- For some questions you can enter a number or something else on the dotted line.
- You cannot give wrong answers.

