**Question 8b. Quels types de médecins avez-vous consultés à l'hôpital au cours des trois derniers mois ? Et à quelle fréquence ?**

Quel type de médecin avez-vous consulté à l'hôpital ?	À quelle fréquence avez-vous consulté ce médecin au cours des trois derniers mois ?
exemple cardiologue	exemple 2 fois
.....	.....fois

.....	.....fois
.....	.....fois
.....	.....fois
.....	.....fois
.....	.....fois
.....	.....fois

**Question 9a. Avez-vous été à nouveau hospitalisé au cours des trois derniers mois ? Vous avez donc dû passer la nuit à l'hôpital.**

- Non
- Oui

Vous avez coché « Oui » ? Vous devez alors répondre aux questions 9b. Si vous avez coché « Non », vous pouvez passer à la question 10.

**Question 9b. Pendant combien de temps êtes-vous hospitalisé(e) ?** Avez-vous été hospitalisé plus d'une fois au cours des trois derniers mois ? Additionnez ensuite tous les jours.

..... jours au total au cours des 3 derniers mois

**Question 10a. Avez-vous été autre part pour recevoir des soins au cours des trois derniers mois ?** Vous avez, par exemple, été dans un centre de soins/résidentiel ou une institution psychiatrique. Ou dans un centre de réhabilitation.

- Non
- Oui, mais je n'y suis allé que pendant la journée.
- Oui, j'y été admis (j'y ai passé la nuit).

Vous avez coché « Oui » ? Vous devez alors répondre aux questions 10b et 10c. Si vous avez coché « Non », c'était la dernière question.

**Question 10b. De quel type d'institution s'agissait-il ?** Cochez la réponse adéquate. Vous pouvez cocher plusieurs réponses.

- Centre de soins résidentiels ou maison de retraite
- Centre de réhabilitation
- Institution de santé mentale
- Autre institution, à savoir .....

**Question 10c. Combien de fois avez-vous rendu visite à cette/ces institution(s) au cours des trois derniers mois ?** Vous avez coché plusieurs réponses à la question 10b ? Veuillez indiquer alors le nombre de jours et de nuits que vous avez visité ces institutions ci-dessous.

- Centre de soins résidentiels ou maison de retraite: ..... jours et ..... nuits au cours des trois derniers mois
- Centre de réhabilitation: ..... jours et ..... nuits au cours des trois derniers mois
- Institution de santé mentale: ..... jours et ..... nuits au cours des trois derniers mois
- Autre institution: ..... jours et ..... nuits au cours des trois derniers mois

C'était la dernière question.

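### English and French iMCQ question 10c asks for a number of visits but records days and nights, and no language version says what counts as a day

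*Protocol*

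**What the plan says.** Section 10.5 of the protocol states that "costs for any other relevant healthcare resource use will be measured by a set of questions from the iMTA Medical Consumption Questionnaire". The questionnaire is reproduced in Dutch (17.7), English (17.8) and French (17.9). In each version, question 10 is the only item on care in rehabilitation centres, nursing homes and similar institutions.

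Question 10a asks whether the patient went to such an institution and offers two positive answers: "Yes, but I only went during the day", or admission with an overnight stay. Question 10b lets the respondent tick several types of institution. Question 10c then collects the amount of care.

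In English, 10c asks "How many times did you have to go here in the past 3 months". Respondents who ticked more than one box in 10b are told: "Then enter the number of days and nights you have been there for each institution below". Every answer line ends with the printed units "days and ..... nights in the past 3 months". The French 10c opens in the same way: "Combien de fois avez-vous rendu visite à cette/ces institution(s) au cours des trois derniers mois". The Dutch 10c asks how long the patient was in the institution and tells anyone with repeat stays to add up all days and nights.

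The English general instructions say: "For each question, tick 1 box, except if the question states that you can tick more than 1 box". The French instructions contain the same rule. The Dutch instructions do not.

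**The concern.** A stem that asks for a number of visits and a field that takes a duration invite different answers to the same item. A patient with one long rehabilitation stay, who ticked one institution, is asked in English or French how often and receives no written instruction to give a duration. Only the units printed on the line point that way. A Dutch-speaking patient with the same stay is asked how long.

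In addition, the word for days is undefined in all three versions. An inpatient may read it as every day spent there, or as days without an overnight stay. The two readings give different quantities of day care for the same history.

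At stake is the count of institutional care units in the cost-effectiveness analysis, which section 2 lists under the tertiary objective. A mistaken entry cannot always be recognised afterwards, because the form does not show which reading the patient used.

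**Working it through.** No figure in the protocol can be reproduced here. The check is a comparison of the three versions, followed by one small example.

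| Element | Dutch (17.7) | English (17.8) | French (17.9) |
|---|---|---|---|
| What 10c asks | duration | number of times | number of times |
| Answer lines in 10c | days and nights, per institution | same | same |
| Who is told to enter a duration | everyone, by the question itself | only those with more than one tick in 10b | only those with more than one tick in 10b |
| Definition of a day in 10c | none | none | none |
| General one-tick rule, covering 10a | none stated | yes | yes |
| Several institutions allowed in 10b | yes | yes | yes |

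**Step 1: question against field.** The two conflict in English and French and agree in Dutch. The version history records that the questionnaires were revised in version 2.4 so that the languages match, so a common question is evidently the aim.

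**Step 2: what counts as a day.** Elsewhere the questionnaire avoids overlap. Question 8a excludes overnight stays in all three languages, and 9b uses a single unit, days. Question 10c has two units and no rule for separating them.

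**Step 3: example with assumed stays.** Suppose a patient spends 20 nights in a rehabilitation centre and then makes 10 day visits to the same centre.

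- If days means day visits only, the entry is 10 days and 20 nights.
- If days includes inpatient days, the entry is about 10 + 20 = 30 days and 20 nights.

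The day count differs by a factor of about 30 / 10 = 3 for identical care.

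**Step 4: can the analyst recover the truth?** Take the natural rule that nights are inpatient care and that only days in excess of nights are day visits.

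- Entry of 30 days and 20 nights under the inclusive reading: 30 − 20 = 10 day visits, which is correct.
- Entry of 10 days and 20 nights under the exclusive reading: 10 − 20 is negative, so the entry can be flagged and queried.
- Entry of 30 days and 20 nights from a patient who used the exclusive reading and made 30 day visits: the rule again gives 10, and nothing on the form shows the error.

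The rule resolves or flags the first two cases but not the third.

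**Step 5: does 10a help?** In English and French it does not. A patient who was admitted and later attended by day may tick only one of the two positive answers, so 10a cannot show that both kinds of care took place.

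**The case against.** The strongest reply is that the form still collects usable units. Question 10a only routes the respondent, because either positive answer leads to 10b and 10c. Question 10b accepts several institutions, and 10c prints separate day and night fields for each. A careful respondent can enter everything, and a costing rule in the analysis plan would handle most entries. This stands. A reader might infer that rehabilitation and nursing-home stays cannot be costed at all, and the documents do not support that. What remains is unreliable reporting: the Step 4 rule does not settle every case, and a visit count entered in place of a duration may not be recognisable.

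A reader might also attach a size to the error. One 42-night stay entered as 1 would lose 1 − 1/42 = 98% of it. Counting each inpatient day a second time as day care would add 30% to 60% if a day unit cost 0.3 to 0.6 of an inpatient day. The stay, the misreading and the cost ratio are all assumed. The protocol gives no unit costs and no rate of misreading.

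Nor is an effect on the difference between arms established. In the registry figures of section 4.5, mRS 4 or 5 makes up 17.2 + 8.0 = 25.2% under deferred treatment and 12.3 + 5.0 = 17.3% under immediate stenting. Those are disability shares, not institutional care, and a single factor would multiply the cost difference only if every respondent made the same error. Randomisation is stratified by centre (section 8.2), so language should be roughly balanced between arms. That makes a systematic tilt unlikely, although the totals and the difference can still be distorted.

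It is also tempting to say that the fault undermines the case for non-inferiority. Section 4.5 expects savings from avoiding a second hospitalisation for carotid revascularisation. Readmission is asked in question 9, which does not have this fault.

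Finally, section 20 plans linkage to Belgian insurance data. This may serve as a cross-check for Belgian patients, but it needs separate authorisation. No Dutch equivalent is described, and coverage of each institution type is not stated.

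**Conclusion.** The concern holds as a measurement fault in one questionnaire item. The conflict between question and field, and the incomplete instruction, are confirmed in English and French and absent from Dutch. The undefined day affects all three versions. The one-tick limit on 10a is established for English and French only.

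The consequence is possible misreporting of rehabilitation and nursing-home use, with different questions pooled across languages in one cost analysis. The threefold spread in the example rests on assumed stays and shows only that the ambiguity is not trivial for a patient who has both kinds of care. The overall error depends on how many patients are affected and how they read the form, and the protocol gives neither. The primary endpoint and the safety analyses are untouched. Severity: minor.

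**What to change.** 1. Reword the English and French 10c to ask how long the patient was in the institution, as the Dutch does.
2. Give the instruction to enter days and nights to every respondent, not only to those with several institutions.
3. In all three versions, label the two fields per institution as nights admitted and as day visits without an overnight stay.
4. Let 10a accept both positive answers, and say so in the question.
5. For forms already returned, fix one rule: cost nights as inpatient stay, cost only days in excess of nights as day visits, and query implausible entries, such as fewer days than nights or a long stay entered as 1. Report a sensitivity analysis under the other reading of days.

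The same edit can correct two routing slips: English 10a sends respondents to a question 11 that does not exist, and Dutch 10c refers to 11b where 10b is meant.

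The cost is a minor questionnaire amendment in three languages and one costing rule. The drawback is that earlier forms will depend on the derivation rule, so the form version should be recorded with each response.

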**That was the last question.**

**Do you have questions or comments?**  
If you have any questions or comments, list them here.

.....  
.....  
.....  
.....  
.....

**Thank you!**

## Questions sur votre consommation en soins de santé

Les chercheurs appellent ce questionnaire l'iMTA MCQ (iMCQ).

### **Instructions**

**Veuillez lire ceci avant de commencer !**

#### **Vous n'êtes pas en mesure de remplir le questionnaire vous-même ?**

Si vous n'êtes pas en mesure de remplir le questionnaire vous-même, une autre personne peut vous y aider. Par exemple, un membre de la famille.

#### **De quoi traite ce questionnaire ?**

Le questionnaire étudie votre utilisation de soins au cours des trois derniers mois.

#### **Combien faut-il de temps pour remplir le questionnaire ?**

Compléter ce formulaire vous prendra environ 20 minutes.

#### **Comment devez-vous remplir le questionnaire ?**

- Commencez par la première question et suivez l'ordre des numéros.
- Pour chaque question, cochez une seule case, sauf si la question indique explicitement que vous pouvez cocher plusieurs cases.
- Pour certaines questions, vous pouvez écrire un nombre ou quelque chose d'autre sur la ligne en pointillés.
- Aucune réponse n'est mauvaise.

#### **Comment vos réponses sont-elles utilisées ?**

Vos réponses sont utilisées pour la recherche. Seuls les chercheurs verront vos réponses. Cela veut donc dire que personne d'autre n'y aura accès . Les chercheurs n'écriront votre nom nulle part. Et ils ne diront à personne que vous avez participé à ce projet de recherche.

**Nous vous remercions pour votre collaboration avec ce questionnaire !**

## Questions sur votre consommation en soins de santé

### Commentaire

Nous aimerions savoir quels médecins vous avez consultés au cours des trois derniers mois. Nous faisons référence aux consultations pour vous-même. Les autres prestataires de soins doivent aussi être comptabilisés. Les physiothérapeutes, par exemple.

Quelles consultations doivent être prises en compte

- Visites de contrôle
- Consultations en raison d'un problème physique ou psychologique
- Consultations pour lesquelles votre médecin est venu chez vous
- Consultations par téléphone
- Appels téléphoniques avec la ligne des ordonnances

Quelles consultations ne doivent pas être prises en compte ?

- Consultations pour une autre personne, par exemple pour votre enfant
- Appels téléphoniques pour prendre un rendez-vous

Vous n'êtes pas certain(e) du nombre de consultations ? Veuillez indiquer approximativement combien de consultations vous avez effectuées.

**Question 1a. Avez-vous consulté un médecin généraliste au cours des trois derniers mois ?**

- Non  
 Oui

Vous avez coché « Oui » ? Vous devez alors répondre à la question 1b.  
Si vous avez coché « Non », vous pouvez passer à la question 2.

**Question 1b. Combien de consultations avez-vous effectuées avec votre médecin traitant au cours des trois derniers mois ?**

- ..... consultations avec le médecin traitant

**Question 2. Combien de consultations avez-vous effectuées avec un physiothérapeute au cours des trois derniers mois ? Ou avec un thérapeute César, un thérapeute Mensendieck ou un thérapeute manuel ?** Ajoutez toutes les consultations avec de tels thérapeutes.

- Aucune consultation  
 ..... consultations

**Question 3. Combien de consultations avez-vous effectuées avec un ergothérapeute au cours des trois derniers mois ?**

- Aucune consultation  
 ..... consultations

**Question 4. Combien de consultations avez-vous effectuées avec un orthophoniste au cours des trois derniers mois ?**

- Aucune consultation
- ..... consultations

**Question 5. Combien de consultations avez-vous effectuées avec un psychologue au cours des trois derniers mois ? Ou avec un psychothérapeute ou un psychiatre ?** Ajoutez toutes les consultations avec ces prestataires de soins.

- Aucune consultation
- ..... consultations

**Question 6a. Avez-vous reçu des soins à domicile au cours des trois derniers mois ?**

- Non
- Oui

Vous avez coché « Oui » ? Vous devez alors répondre aux questions 6b à 6d. Si vous avez coché « Non », vous pouvez passer à la question 7.

**Question 6b. Quel type de soins à domicile avez-vous reçus au cours des trois derniers mois ?** Vous pouvez cocher plusieurs réponses.

- Entretien de la maison et aide ménagère  
*exemples : passer l'aspirateur, faire le lit, aller faire des courses*
- Soins personnels  
*exemples : aide pour prendre un bain ou s'habiller*
- Soins infirmiers  
*exemples : faire un bandage, administrer des médicaments, mesurer la tension artérielle*

**Question 6c. Pendant combien de semaines avez-vous fait appel à ce type de soins à domicile ?** Comptez toutes les semaines au cours des trois derniers mois.  
*Remarque : une période de trois mois comprend treize semaines.*

Aide ménagère : ..... semaines au cours des trois derniers mois

Soins personnels : ..... semaines au cours des trois derniers mois

Soins infirmiers : ..... semaines au cours des trois derniers mois

**Question 6d. Combien d'heures de soins à domicile avez-vous reçues en moyenne au cours de ces semaines ?**

Aide ménagère : en moyenne ..... heures par semaine

Soins personnels : en moyenne ..... heures par semaine

Soins infirmiers : en moyenne ..... heures par semaine

**Question 7a. Avez-vous pris des médicaments anticoagulants\* au cours des trois derniers mois ?**

Non

Oui

\* carbasalaatcalcium (ascal, acetylsalicylzuur), clopidogrel (plavix, grepid, iscover), prasugrel (efient) , ticagrelor (brilique), dipyidamol (persantin), acenocoumarol (sintrom), fenprocoumon (marcoumar), dabigatran (pradaxa), rivaroxaban (xarelto), apixaban; (eliquis), edoxaban (lixiana)

Vous avez coché « Oui » ? Vous devez alors répondre à la question 7b et dresser une liste des médicaments que vous avez utilisés avec la quantité administrée. Si vous avez coché « Non », vous pouvez passer à la question 8.

**Question 7b. Quels médicaments anticoagulants avez-vous pris au cours des trois derniers mois ?** Les médicaments anticoagulants comprennent tous les types de médicaments énumérés à la question 7a après l'astérisque (\*). Vous pouvez retrouver deux exemples ci-dessous.

**Attention** : lisez attentivement la posologie ! Elle indique combien vous avez dû en prendre à chaque fois. Et la fréquence avec laquelle vous avez dû le faire chaque jour. **Vous avez utilisé plus ou moins ? Veuillez alors indiquer la quantité réellement utilisée.**

Quel est le nom des médicaments ?	Combien en avez-vous pris à chaque fois ? Regardez la posologie	Combien de fois en avez-vous pris par jour ? Regardez la posologie	Combien de jours au cours des trois derniers mois avez-vous utilisé le médicament ?
exemple 1 carbasalaatcalcium	exemple 100 mg	exemple 1 fois	exemple 14 jours

exemple 2	exemple	exemple	exemple
Clopidogrel	75 mg	1 fois	90 jours
.....	.....	.....	.....
.....	.....	.....	.....
.....	.....	.....	.....
.....	.....	.....	.....
.....	.....	.....	.....
.....	.....	.....	.....
.....	.....	.....	.....
.....	.....	.....	.....

**Question 8a. Avez-vous eu une consultation à la polyclinique de l'hôpital au cours des trois derniers mois ?** Il s'agit de consultations pour vous-même avec un médecin. Par exemple avec un cardiologue, un rhumatologue ou un neurologue.

Autrement dit, sans passer de nuit à l'hôpital

- Non  
 Oui

Vous avez coché « Oui » ? Vous devez alors répondre à la question 8b sur les types de médecins que vous avez consultés. Et à propos de la fréquence. Vous pouvez retrouver un exemple à la première ligne.

Si vous avez coché « Non », vous pouvez passer à la question 9.

**Question 8b. Quels types de médecins avez-vous consultés à l'hôpital au cours des trois derniers mois ? Et à quelle fréquence ?**

Quel type de médecin avez-vous consulté à l'hôpital ?	À quelle fréquence avez-vous consulté ce médecin au cours des trois derniers mois ?
exemple cardiologue	exemple 2 fois
.....	.....fois

.....	.....fois
.....	.....fois
.....	.....fois
.....	.....fois
.....	.....fois
.....	.....fois

**Question 9a. Avez-vous été à nouveau hospitalisé au cours des trois derniers mois ? Vous avez donc dû passer la nuit à l'hôpital.**

- Non
- Oui

Vous avez coché « Oui » ? Vous devez alors répondre aux questions 9b. Si vous avez coché « Non », vous pouvez passer à la question 10.

**Question 9b. Pendant combien de temps êtes-vous hospitalisé(e) ?** Avez-vous été hospitalisé plus d'une fois au cours des trois derniers mois ? Additionnez ensuite tous les jours.

..... jours au total au cours des 3 derniers mois

**Question 10a. Avez-vous été autre part pour recevoir des soins au cours des trois derniers mois ?** Vous avez, par exemple, été dans un centre de soins/résidentiel ou une institution psychiatrique. Ou dans un centre de réhabilitation.

- Non
- Oui, mais je n'y suis allé que pendant la journée.
- Oui, j'y été admis (j'y ai passé la nuit).

Vous avez coché « Oui » ? Vous devez alors répondre aux questions 10b et 10c. Si vous avez coché « Non », c'était la dernière question.

**Question 10b. De quel type d'institution s'agissait-il ?** Cochez la réponse adéquate. Vous pouvez cocher plusieurs réponses.

- Centre de soins résidentiels ou maison de retraite
- Centre de réhabilitation
- Institution de santé mentale
- Autre institution, à savoir .....

**Question 10c. Combien de fois avez-vous rendu visite à cette/ces institution(s) au cours des trois derniers mois ?** Vous avez coché plusieurs réponses à la question 10b ? Veuillez indiquer alors le nombre de jours et de nuits que vous avez visité ces institutions ci-dessous.

- Centre de soins résidentiels ou maison de retraite: ..... jours et ..... nuits au cours des trois derniers mois
- Centre de réhabilitation: ..... jours et ..... nuits au cours des trois derniers mois
- Institution de santé mentale: ..... jours et ..... nuits au cours des trois derniers mois
- Autre institution: ..... jours et ..... nuits au cours des trois derniers mois

C'était la dernière question.

